	Confirm availability of pretreatment tumor tissue		X		If archived tissue is not available, a fresh tumor biopsy should be obtained after all other study entry criteria have been confirmed, unless the sponsor and investigator document that the patient may be enrolled without pre-treatment tissue.
	Exploratory blood sample for biomarkers			X	
	Optional pretreatment biopsy		X		Optional and may be performed at any time before starting treatment with LY2606368. See Section 9.8.2.
Health Outcome Measure	Lung Cancer Symptom Scale		X		The LCSS should be administered prior to extensive interaction with site personnel.

Schedule of Screening Activities

Abbreviations: BL = baseline; CTCAE = Common Terminology Criteria for Adverse Events (NCI 2009);
ECG = electrocardiogram; ECOG = Eastern Cooperative Oncology Group (Oken et al. 1982); LCSS = Lung
Cancer Symptom Scale; RECIST 1.1 = Response Evaluation Criteria In Solid Tumors Version 1.1 (Eisenhauer
et al. 2009).

Table JTJH.2.2. On-Study-Treatment Schedule of Activities

Study Period		Study Treatment Period						Comments
		1		2		3-n ^a		
Cycle/Visit		14 days		14 days		14 days		
Duration		14 days		14 days		14 days		
Relative Day within Dosing Cycle		1	8	1	8	1	8	
Procedure Category	Procedure							
Physical Examination	Physical Exam	X		X		X		Includes weight and calculated BSA. May be completed up to 7 days prior to treatment infusion. In Cycle 4 and beyond may be completed every other cycle (for example, Cycle 4, 6, 8, etc.).
	Vital signs	X		X		X		Includes blood pressure, pulse, and temperature. Complete before treatment infusion.
	ECOG performance status	X		X		X		Complete before treatment infusion.
Laboratory/ Diagnostic Tests	Hematology	X	X	X	X	X	X	May be drawn up to 3 days before the planned assessment. In Cycles 4-n, the Day-8 sample may be collected at the discretion of the investigator.
	Chemistry	X		X		X		May be drawn up to 3 days before the planned assessment.
	Urinalysis					X		May be collected up to 3 days before the planned assessment.
	Urine pregnancy test					X		Day 1 of every other cycle. Only to be performed on women of childbearing potential.
	PK sampling	X	X	X		X	X	See PK Schedule for collection information.
	Stored sample for pharmacogenetics	X						Collect once. Sample can be collected at any time if not collected on Day 1 of Cycle 1.
	Exploratory blood sample for biomarkers						X	Only to be collected on the same day when the CT scan is obtained (every 3 cycles starting with Cycle 3).

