3.2.1. Prior Clinical Experience with LY2606368 as a Monotherapy: Study JTJA

LY2606368 was assessed as a monotherapy for patients with solid tumors and demonstrated an acceptable safety/tolerability profile, with transient neutropenia being the primary toxicity.

As of 27 August 2015, data were available from 146 patients who were treated with LY2606368 on Days 1, 2, and 3, or on Day 1 only of a 14-day schedule. The maximum tolerated dose (MTD) of LY2606368 administered on Days 1, 2, and 3 every 14 days was determined to be 40 mg/m², and the MTD of LY2606368 when administered on Day 1 every 14 days was determined to be 105 mg/m². A dose of 105 mg/m² once every 14 days was selected as the recommended Phase 2 dose for monotherapy.

In patients who have received 105 mg/m² of LY2606368, neutropenia was the most frequent and severe toxicity following treatment with LY2606368. Grade 4 decreases in neutrophils deemed related to LY2606368 treatment were observed in 71% of these patients. In general, neutrophil counts nadir on Day 8 and Grade 4 decreases were often less than 5 days. Grade 4 decreases in platelets were observed in 5.7% of patients. Grade 4 anemia was not observed. Nonhematologic toxicity occurred at a lower frequency than hematologic toxicity and was predominantly Grade 1 in severity.

In the 105 patients who received LY2606368 at a dose of 105 mg/m² once every 2 weeks, the treatment-related AEs most frequently reported following LY2606368 treatment in Study JTJA include neutrophil count decreased (93%), platelet count decreased (46%), anemia (33%), white blood cell decreased (30%), fatigue (28%), nausea (14%), febrile neutropenia (11%), and headache (11%).

Please see the Investigator's Brochure (IB) for additional information on the nonclinical and clinical experience with LY2606368.

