7.2.1. Selection and Timing of Doses

A cycle is defined as an interval of 14 days. A delay of a cycle (Day 1) due to holiday, weekend, inclement weather, or other unforeseen circumstances will be permitted for a maximum of 7 days and not counted as a protocol deviation. An interval of at least 14 days must be maintained between LY2606368 doses, and if there is a delay the cycle length should be extended to accommodate the delay.

The actual doses of LY2606368 to be administered will be determined by calculating the patient's body surface area (BSA) at the beginning of each cycle. If the patient's weight does not fluctuate by more than $\pm 10\%$ from the weight used to calculate the prior dose, the BSA will not need to be recalculated. A $\pm 10\%$ variance in the calculated total dose will be allowed for ease of dose administration.

A patient may continue to receive LY2606368 until he or she meets 1 or more of the specified reasons for discontinuation (as described in Section 8).

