5.13.4. Clinical Laboratory Evaluation

Laboratory data (hematology, chemistry) will be listed for all patients on therapy. Abnormal results will be listed separately for all patients on therapy.

In addition to the investigator-reported AEs, all relevant hematology and chemistry laboratory values will be graded according to CTCAE version 4.0. These derived values will be included on the listings of laboratory data and summary tables will be produced in a similar manner to those created for the investigator reported AEs.

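### The Day 8 blood count may be drawn up to three days early, ahead of the neutrophil nadir the protocol reports, so a compliant draw can miss short Grade 4 neutropenia

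*Protocol*

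**What the plan says.** Table JTJH.2.2 marks hematology on Day 1 and Day 8 of Cycle 1, Cycle 2 and Cycles 3 onward. The row has a single timing comment: "May be drawn up to 3 days before the planned assessment. In Cycles 4-n, the Day-8 sample may be collected". The rest of that sentence leaves the later Day 8 samples to the investigator's judgment. The early allowance is not limited to Day 1, and nothing is allowed after the planned day.

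Protocol Section 3.2.1 summarizes the earlier monotherapy study at the same dose: "In general, neutrophil counts nadir on Day 8 and Grade 4 decreases were often less than 5 days". It also reports that "Grade 4 decreases in neutrophils deemed related to LY2606368 treatment were observed in 71% of these patients", and it names transient neutropenia as the primary toxicity.

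SAP 5.13.4 says that "all relevant hematology and chemistry laboratory values will be graded according to CTCAE version 4.0", with summary tables produced like those for investigator-reported adverse events. Characterizing safety and toxicity, including laboratory tests, is a secondary objective.

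**The concern.** An early draw makes sense for Day 1, when the result is needed before dosing. Chemistry and urinalysis carry much the same three-day allowance, but neither is scheduled on Day 8. Hematology is the only row with this allowance that also has a Day 8 sample, and the protocol gives no reason for drawing that sample early. The wording looks like a Day 1 rule that also reaches Day 8.

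The Day 8 count is the only scheduled count near the reported nadir. If it is taken on Day 5 or 6, a Grade 4 decrease of a few days may not yet have begun. Sites with different visit habits would then feed non-comparable values into one table of laboratory-graded neutropenia.

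From Cycle 4 the Day 8 count is optional, so later near-nadir values come from a selected set of patients. Pooling them with the mandatory counts of Cycles 1–3 mixes two kinds of data.

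**Working it through.** The plan states no detection rate, so there is no figure to reproduce. The check is interval arithmetic.

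**Inputs from the documents**
- Planned day 8, early allowance 3 days, no late allowance (Table JTJH.2.2). Compliant draw days run from 8 − 3 = 5 to 8.
- Nadir on Day 8 in general; Grade 4 often under 5 days (Section 3.2.1).
- Cycle length: "A cycle is defined as an interval of 14 days" (Section 7.2.1). The next scheduled count is the next Day 1, which is Day 15, or Day 15 − 3 = Day 12 at the earliest.

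**Assumptions, because the documents give no distribution**
- Each Grade 4 episode includes Day 8. A Day 8 draw therefore captures 100% by construction.
- Episode length d is uniform on 1 to 5 days.
- Placement is either (a) centred on Day 8 or (b) with onset uniform over the d days up to Day 8.

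**Formulas.** Let s be the draw day and k = 8 − s.
- (a) The episode is seen if d ≥ 2k. For k = 3, 2, 1 this needs d ≥ 6, 4, 2, with probabilities 0, (5 − 4)/4 = 0.25 and (5 − 2)/4 = 0.75.
- (b) For given d, the probability is max(0, (d − k)/d). Averaged over d:
  - k = 3: (2 − 3 ln(5/3))/4 = 0.12
  - k = 2: (3 − 2 ln 2.5)/4 = 0.29
  - k = 1: (4 − ln 5)/4 = 0.60

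| Draw day | (a) centred | (b) uniform onset |
|---|---|---|
| 5 | 0% | 12% |
| 6 | 25% | 29% |
| 7 | 75% | 60% |
| 8 | 100% | 100% |

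For fixed lengths under (b), a Day 5 draw captures 0% for d ≤ 3, 25% for d = 4 and 39% for d = 4.9.

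**Is there a later scheduled count to catch the episode?** Under (a), an episode shorter than 5 days ends before 8 + 2.5 = Day 10.5, so even a Day 12 draw is too late. Under (b), only an episode longer than 4 days could reach Day 12. The next pre-dose count is therefore little or no backup.

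**What limits the exposure.** Protocol Appendix 4 schedules a PK sample on Day 8 of Cycles 1, 3 and 5. Two of the three mandatory Day 8 counts (Cycles 1 and 3) thus coincide with another Day 8 draw, and Cycle 2 does not. The PK schedule does not narrow the hematology window, but it gives a reason to attend on Day 8.

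**The case against.** The strongest case on the other side is that the window is permissive and the likely behaviour is benign. Day 8 is the same weekday as the infusion, PK sampling brings patients in on Day 8 of Cycles 1, 3 and 5, and patients who stay on treatment have three mandatory Day 8 counts. SAP 5.13.4 grades all relevant values, so unscheduled counts can contribute, and investigator-reported events are tabulated separately. The SAP sets no nadir-neutropenia rate, threshold or comparison with the earlier study. Optional Day 8 sampling from Cycle 4 was introduced on purpose by Amendment (a). All of this stands. It lowers the expected loss, but it does not remove the mismatch between the schedule and Section 3.2.1.

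Three stronger readings are tempting, and the documents do not support them.

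- **That the observed Grade 4 rate would fall from 71% to about 36%.** This multiplies 0.71 by 0.50, the mean one-cycle capture if draws spread evenly over Days 5–8. But 71% is a per-patient proportion already observed in the earlier study, not a true per-cycle rate. If episodes recurred and draw days were independent, three cycles at 50% would give 1 − 0.5³ = 88% capture, or 0.71 × 0.88 = about 62%. That too is only an illustration; a site that always draws early would gain less. The 36% also treats every episode as short, where Section 3.2.1 says only that many are, and the even spread ignores the Day 8 PK draws.
- **That early sampling can only lower the rate.** The nadir is on Day 8 in general, not always. An episode that ends before Day 8 would be caught only by an earlier draw.
- **That dosing or supportive care is compromised.** Cycle start depends on pre-cycle counts. Dose reduction and growth-factor use rest on the investigator's judgment. None is tied to a Day 8 value.

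**Conclusion.** The concern holds as a mismatch within the protocol. Table JTJH.2.2 allows the Day 8 count on Days 5–7, while Section 3.2.1 puts the nadir in general on Day 8 with Grade 4 decreases often under 5 days. A compliant early draw can miss short Grade 4 neutropenia, and the laboratory-graded tables then depend partly on site visit timing.

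That the schedule permits this is clear from the text. That a later draw falls outside the window is an inference, because no late allowance is given and a late draw is not expressly forbidden.

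The size is unknown. One-cycle capture of about 0–12% on Day 5, rising to 100% on Day 8, rests on the assumed length and placement of episodes. If every site draws on Day 8, episodes spanning that day are not lost. The realistic loss is probably well short of the worst case and falls mainly on Cycle 2, the mandatory Day 8 count without a PK draw.

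The effect is confined to descriptive safety data. ORR, the futility rule and the final decision rule are untouched. The change is worth making because it is cheap and neutropenia is the main expected toxicity.

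**What to change.** In Table JTJH.2.2, reconcile the hematology comment with Section 3.2.1: limit the three-day early allowance to the Day 1 pre-dose count, and give the Day 8 count its own sampling window consistent with the stated nadir. The width is for the sponsor to set.

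In SAP 5.13.4, summarize laboratory-graded neutropenia for Cycles 1–3, where the Day 8 count is mandatory, separately from Cycle 4 onward, where it is discretionary.

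The cost is one schedule comment, one SAP sentence, one extra table split and slightly less scheduling freedom around Day 8. No additional blood sample is needed.

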	Plasma biomarker sample	X				X		Collect prior to dosing on Day 1 of Cycles 1 and 3 only.
	ECG	X		X		X		Single local ECG collected at each time point. Day 1: predose, 10 min after EOI (±5 min), 30 min after EOI (±10 min), and >1 hour after EOI. Cycle 2-X: predose. However, if QTcF >480 msec is observed on Day 1, then 10 min after EOI (±5 min), 30 min after EOI (±10 min), and >1 hour after EOI should also be collected in subsequent cycles.
Optional Tumor Biopsy			X				Can occur at any time during patient's treatment.	

Study Period		Study Treatment Period						
		1		2		3-n ^a		
Cycle/Visit		14 days		14 days		14 days		
Duration		14 days		14 days		14 days		
Relative Day within Dosing Cycle		1	8	1	8	1	8	
Tumor Assessment	Radiologic imaging according to RECIST 1.1						X	For the first 52 weeks following enrollment, perform approximately every 6 weeks starting at the end of Cycle 3 (eg, Days 8-14). Thereafter, perform approximately every 12 weeks. The scanning interval (6 or 12 weeks [± 1 week]) should be maintained even if cycles are delayed. As a result, after Cycle 3, the scans may not always occur at the end of a cycle. The same method of imaging used at baseline should be used for each subsequent assessment. Scans should also be obtained as clinically indicated.
Tumor Assessment	Tumor measurement (palpable or visible)						X	Perform at least every 6 weeks starting in Cycle 3 on the same day as the radiologic imaging.
Adverse Events Collection/ CTCAE Grading		X		X		X		
Concomitant Medication Notation		X		X		X		
Lung Cancer Symptom Scale		X		X		X		The LCSS is to be administered prior to extensive interaction with site personnel and prior to administration of study drug.
Study Treatment	LY2606368	X		X		X		IV over approximately 60 (+10) min

Abbreviations: BSA = body surface area; CT = computed tomography; CTCAE = Common Terminology Criteria for Adverse Events (NCI 2009); ECG = electrocardiogram; ECOG = Eastern Cooperative Oncology Group (Oken et al. 1982); EOI = end of infusion; IV = intravenous; min = minute; LCSS = Lung Cancer Symptom Scale; PK = pharmacokinetic; QTcF = QT interval using Fridericia’s correction; RECIST 1.1 = Response Criteria In Solid Tumors Version 1.1 (Eisenhauer et al. 2009).

Table JTJH.2.3. Post-Treatment Follow-Up Schedule of Activities

Study Period		Post-discontinuation Follow-Up		
		Short-term Follow-Up	Long-term Follow-Up	
Duration		30 ± 5 days	60 ± 14 days	
Visit		801	802-X	

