9.4. Safety

9.4.1. Other Safety Measures

For each patient, safety assessments, including ECGs, vital signs, and laboratory tests, should be collected as shown in the Schedule of Activities (Section 2). ECGs should be recorded according to the study-specific recommendations that will be provided separately.

As of 27 August 2015, no patients treated with LY2606368 monotherapy have had an average QTcF interval >480 msec at any time point. However, if a patient experiences a QTcF interval >480 msec, the patient should be monitored for signs of life-threatening arrhythmias such as torsades de pointes. It should be confirmed that the measurement is correct by repeating the ECG and ruling out other causes such as atrial fibrillation or the presence of a pacemaker. If the result is confirmed, institutional guidelines or standard of care measures for management of QTcF interval >480 msec and/or associated arrhythmias should be initiated. These actions may include the administration of IV magnesium sulfate and the assessment of clinical chemistry. If electrolytes are abnormal, they should be repeated as indicated. The QTcF value should be monitored until the interval has returned to <480 msec or at least to predose levels. It is recommended that the patient be assessed by a cardiologist before leaving the treating facility. For all subsequent doses, an ECG must be obtained at 10 minutes after the end of infusion (EOI) (± 5 minutes), 30 minutes after EOI (± 10 minutes), and >1 hour after EOI.

If a patient experiences a QTcF interval >500 msec and has an associated life-threatening arrhythmia, he/she should be discontinued from study treatment. If a patient experiences a QTcF interval >500 msec without an associated life-threatening arrhythmia and if the investigator deems it in the best interest of the patient, the patient may continue treatment with LY2606368. If a patient has a second occurrence of QTcF interval >500 msec, he/she should be discontinued from study treatment.

Any clinically significant findings that result in a diagnosis and that occur after the patient receives the first dose of LY2606368 should be reported to Lilly or its designee as an AE via CRF/electronic data entry/designated data transmission methods.

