Appendix 7. Protocol Amendment I4D-MC-JTJH(a) Summary

A Phase 2 Study of LY2606368 in Patients with Extensive Stage Disease Small Cell Lung Cancer

Overview

Protocol I4D-MC-JTJH, A Phase 2 Study of LY2606368 in Patients with Extensive Stage Disease Small Cell Lung Cancer, has been amended. The new protocol is indicated by amendment (a) and will be used to conduct the study in place of any preceding version of the protocol.

This amendment was developed to address requests resulting from member states participating in the Voluntary Harmonisation Procedure during the assessment of the initial clinical trial application for Study JTJH in the European Union. The request resulted in the following changes:

- Inclusion criterion #8 was updated to include a definition for fertile men.
- Inclusion criterion #9 was updated to include a definition of women of childbearing potential and postmenopausal women.
- Exclusion criterion #14 was updated to include known hypersensitivity to LY2606368.
- Exclusion criterion #16 was updated to clarify how patients with HIV or symptomatic activated or reactivated hepatitis A, B, or C would be excluded.
- Text was added to Section 9.4.1 to establish additional actions to be taken in case of prolongation of the QTcF interval >480 msec. Text was also added to provide guidance on patient management if a patient experiences a QTcF interval of >500 sec.

In addition, several other changes were made to the protocol as follows:

- Minor wording changes and clarifications were made to the Schedule of Activities in Section 2.
- A clarification to time to progression was made in Section 3.1.
- Adverse events were corrected for a literature reference in the rationale section.
- The wording for exclusion criterion #11 was clarified.
- A table was added to clarify the parameters required to start each cycle.
- Section 7.5.2 was modified to remove the stability information in the lactate monohydrate formulation.
- Section 7.8.1 was modified to remove the provision that patients must sign new ICFs to enter the continued access period.
- A clarification to the radiologic scans required was made in Section 9.1.
- A clarification to the PK analysis was made in Section 9.5

- A clarification to the biomarker collection was made in Section 9.8.
- Section 10.3.4 was modified to remove the final analysis from the stopping rules.
- Minor editing and formatting changes were made.

Revised Protocol Sections

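### The ECG row of Table JTJH.2.2 has a narrower and softer trigger for later post-infusion ECGs (QTcF >480 msec on Day 1, should) than Section 9.4.1 (no day or cycle limit, must)

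*Protocol*

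**What the plan says.** **Table JTJH.2.2, ECG row (Protocol Section 2).** On Day 1 the row asks for a predose ECG and three post-infusion ECGs. For later cycles it says: "Cycle 2-X: predose. However, if QTcF >480 msec is observed on Day 1, then 10 min after EOI". It then lists the 30-minute time point and ends: ">1 hour after EOI should also be collected in subsequent cycles". The row does not refer to Section 9.4.1.

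**Protocol Section 9.4.1.** The trigger carries no day or cycle limit: "if a patient experiences a QTcF interval >480 msec, the patient should be monitored for signs of life-threatening arrhythmias". The site is to have it "confirmed that the measurement is correct by repeating the ECG and ruling out other causes". Management and follow-up instructions come next, and the paragraph ends with the ECG rule: "For all subsequent doses, an ECG must be obtained at 10 minutes after the end of infusion (EOI"), and again at 30 minutes and at more than 1 hour. The following paragraph lets a patient continue after a first value above 500 msec if there is no life-threatening arrhythmia and the investigator judges it in the patient's interest. It then says: "If a patient has a second occurrence of QTcF interval >500 msec, he/she should be discontinued from study treatment".

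**Links between the two.** Section 9.4.1 sends sites to the Section 2 schedule for ECG collection. It also says: "ECGs should be recorded according to the study-specific recommendations that will be provided separately". Those recommendations are not among the documents.

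**Background.** Appendix 7 reports: "Text was added to Section 9.4.1 to establish additional actions to be taken in case of prolongation of the QTcF interval" beyond 480 msec. It describes the changes to the schedule as minor wording changes and clarifications.

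**The concern.** Both texts are current and both tell a site what to do at later doses after a QTcF above 480 msec, but they do not describe the same patients. The table ties the extra ECGs to Day 1 and uses *should*. Section 9.4.1 ties them to the event, whenever it occurs, and uses *must*.

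Relying on the schedule is foreseeable, because Section 9.4.1 itself points there for ECG collection and the ECG row does not point back. Other comments in the Section 2 tables do cite protocol sections (6.1, 9.1 and 9.8.2 in Table JTJH.2.1).

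What is at stake is QT monitoring in a patient who has already shown prolongation and is still being dosed. A second value above 500 msec requires discontinuation, and the post-infusion ECGs help to detect it. A predose ECG alone could miss a rise that follows the infusion. Section 7.7 notes that no thorough QTc study has yet been done.

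**Working it through.** The plan states no figure on this point, so there is none to reproduce. The check sets the two rules side by side, counts ECGs in two worked cases, and bounds the number of patients.

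**1. The two rules**

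| Feature | Table JTJH.2.2, ECG row | Section 9.4.1 |
|---|---|---|
| When the trigger can occur | Day 1 | No limit stated |
| Confirmation | Observed is enough | Repeat ECG and rule out other causes come before the ECG sentence |
| Strength | Should | Must |
| Post-infusion ECGs per later dose | 3 | 3 |

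The table is narrower on timing and weaker in force, but broader on confirmation.

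**2. What Day 1 means.** The cell gives the full ECG set for Day 1 and then a predose ECG for Cycle 2 onward. Cycle 2 and later ECGs also fall on Day 1 of their cycle. If Day 1 meant Day 1 of any cycle, the two instructions would clash, so Cycle 1 Day 1 is the natural reading. The any-cycle reading remains possible because the column header is the relative day within the dosing cycle.

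**3. Where the rules part**

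- First value above 480 msec on Cycle 1 Day 1: both texts call for 3 post-infusion ECGs at each later dose.
- First value at a predose ECG in Cycle 2 or later: on the natural reading the table adds nothing, while Section 9.4.1 requires 3 per later dose.
- First value on an unscheduled ECG on another day of the cycle: on either reading the table adds nothing, while Section 9.4.1 requires 3 per later dose.

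**4. Counts** (ECGs = 3 × number of later doses; first value assumed confirmed)

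*Example A.* Unscheduled ECG on Cycle 2 Day 8, dose given in Cycle 3. Section 9.4.1: 3 × 1 = 3. Table alone: 0 on both readings. Shortfall 3.

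*Example B.* First value at the Cycle 2 predose ECG, doses given in Cycles 2 and 3.

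| Doses counted as subsequent | Day 1 read as | Section 9.4.1 | Table alone | Shortfall |
|---|---|---|---|---|
| Cycle 3 only | Cycle 1 Day 1 | 3 | 0 | 3 |
| Cycle 3 only | Day 1 of any cycle | 3 | 3 | 0 |
| Cycles 2 and 3 | Cycle 1 Day 1 | 6 | 0 | 6 |
| Cycles 2 and 3 | Day 1 of any cycle | 6 | 3 | 3 |

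Example B therefore runs from 0 to 6. The 6 depends on treating the same-day Cycle 2 dose as a subsequent dose, which is arguable. A site applying both sections has a shortfall of 0 in every row.

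**5. How many patients.** Section 7.7 reports that none of 101 patients on monotherapy in Study JTJA had an average QTcF above 480 msec. The one-sided 95% upper limit for 0 of 101 is 1 − 0.05^(1/101) = 0.0292, or 2.9%. Applied to the planned 116 patients: 0.0292 × 116 = 3.4, about 3. This is indicative only. JTJA reported average QTcF and this study uses single local ECGs. The figure also counts patients first detected on Cycle 1 Day 1, where the texts agree, so the affected group is a subset.

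**The case against.** The strongest reply is that the protocol already contains the right rule. The table says *if*, not *only if*, and forbids nothing that Section 9.4.1 requires, so the two can be applied together. The table also gives no instructions for managing a high QTcF. A site with such a reading would have to turn to Section 9.4.1, where the ECG rule closes the same paragraph. All scheduled on-treatment ECGs fall on Day 1 of a cycle, so on the any-cycle reading the table covers every one of them. Predose ECGs continue in every cycle whichever text is followed, and exclusion criterion 17 removes patients with QTcF above 470 msec on more than one screening ECG.

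Most of this stands and limits the weight of the point. It does not remove the mismatch: the any-cycle reading is the less natural one, and Section 9.4.1 sends sites back to the schedule for ECG collection.

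A reader might go further and make any of these inferences, which the documents do not support:

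- **The two sections contradict each other, or patients will go unmonitored.** A site following Section 9.4.1 takes every required ECG.
- **Section 9.4.1 says at any time.** It simply states no limit, and its ECG sentence follows a confirmation step, so it arguably covers only confirmed values.
- **About 3 patients will be affected.** That figure is an upper limit for a wider group.
- **Nothing holds dosing after a high QTcF.** Section 9.4.1 states no hold at 480 msec, but Section 7.4 requires nonhematologic toxicities to resolve to Grade 0 or 1 or baseline before each cycle, with exceptions. Whether a given QTcF falls under that depends on CTCAE grades that are not in the documents.

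**Conclusion.** The inconsistency is real and worth correcting, but it is small. A site working from the schedule could omit three post-infusion ECGs at each later dose for a patient whose first QTcF above 480 msec comes after Cycle 1 Day 1 or on an unscheduled ECG. For a Cycle 2 or later predose value this rests on reading Day 1 as Cycle 1 Day 1. For an unscheduled value on another day it holds on either reading. Few patients are likely to be concerned, provided average QTcF in JTJA is a fair guide to single local ECGs here. The point affects safety monitoring only.

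One thing stays open: the separately provided ECG recommendations may already settle the trigger, and they could not be checked.

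**What to change.** In the ECG row of Table JTJH.2.2, replace the trigger with wording such as: *if QTcF >480 msec is observed in any cycle, on a scheduled or unscheduled ECG, then ECGs at 10 min (±5 min), 30 min (±10 min) and >1 hour after EOI must also be collected at all subsequent doses (see Section 9.4.1)*.

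Do not add a requirement that the value first be confirmed by repeat ECG. The table now acts on an observed value, and a confirmation condition would remove the existing trigger for Day 1 readings that are not confirmed. Check that the separately provided ECG recommendations carry the same rule.

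The cost is one sentence, at the next amendment or in a letter to sites. The downside is a few extra local ECGs after readings that turn out not to be confirmed.
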